of the P1 to detect AB. A study of AB in non-anxious participants using the MDP task to present fearful and neutral faces found that probes replacing fearful faces produced significantly larger occipital P1 than probes that replaced neutral faces [53]. A similar study of high and low anxious participants, using threatening and neutral pictures, found that P1 to probes were larger to the threatening compared to the neutral pictures only for high anxious individuals [54]. These studies suggest that unpleasant or threatening stimuli are subject to an AB, particularly for anxious individuals. However, another study suggests that normal participants can have AB to pleasant as well as unpleasant stimuli [55], as the P1 to pleasant (baby faces) and unpleasant (anger faces) stimuli were both larger when compared to neutral faces. These studies suggest that P1 reflects a general attentional mechanism that is sensitive to individual differences in AB, making it an ideal procedure for evaluating the impact of ABM on AB on the nicotine dependent.

Preliminary Studies

Multiple-sessions seem to maximize the ABM training effect among heavy drinkers and the alcohol dependent, but no published study has evaluated intensive training in smokers. In-home ABM training may increase the generalization of its effect on AB and smoking behavior. In this section, we review our studies of AB in smokers and our efforts to develop computerized smoking interventions for use outside of the laboratory. Our research group has extensive experience studying attentional and motivational aspects of nicotine dependence. With our preliminary studies, we wish to show that we have experience (a) developing and administering mobile interventions and assessments for use outside of the laboratory; (b) evaluating AB in smokers using RT tasks, (c) assessing in-home AB in smokers trying to quit; and (d) using ERPs as a reliable measure of AB in smokers.

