Laboratory sessions: AB assessment using the MDP task. After completing the smoking behavior assessments, participants will complete an MDP task designed to evaluate AB to smoking compared with neutral pictures. First, they will be fitted with an EEG sensor net (see below), which will take approximately 20 min. The participants will then receive instructions about

Figure 3. The MDP laboratory task

the laboratory AB assessment task and will be notified of the monetary rewards associated with completing each trial accurately and quickly. The participants will complete 8 practice trials involving pictures of abstract art before starting the test trials. Each practice and test trial will begin with a fixation cross at the center of the screen, functioning as an inter-trial interval (ITI) that will vary randomly from 800 to 1200 ms (Figure 3). Participants will be instructed to keep their eyes focused on the fixation cross at all times. After the ITI, two pictures, of smoking and neutral content, will be displayed simultaneously on either side of the fixation cross for 200 ms. The 200 ms stimulus presentation time was chosen because it, unlike the 500 ms presentation used in several other studies, reflects AB in orientation to [89], and not disengagement from [90], substance-related stimuli. The pictures or words then disappear and a probe randomly

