Laboratory sessions: ERP data collection and reduction. The AB assessments completed at the 3 laboratory sessions will involve an ERP measure of attentional processing. The number of ABM trials to be assessed (n=320) was chosen to have an adequate signal-to-noise ratio for measuring the P1 component [50]. EEG will be recorded with a 129-channel net and amplified with an AC-coupled high-input impedance (200 MΩ) amplifier (Geodesic EEG System 250; Electrical Geodesics, Inc., Eugene, OR) referenced to Cz. The sampling rate will be 250 Hz, and data will be filtered online with a 0.1-Hz high-pass filter. After data collection, we will apply a 100-Hz low-pass filter, and interpolate channels contaminated by artifacts for more than 50% of the recording. Eyeblinks will be corrected by using a spatial filtering method [108]. After eyeblink correction, the EEG data will be transformed to the average reference and segmented into 700-ms segments starting 100 ms before onset of the picture or word pair. Baseline will be defined as the 100-ms interval preceding the picture or word pair. Segments with more than 10% of the sensors contaminated will be rejected; otherwise, the contaminated channels will be interpolated. For each session for each participant, we will calculate the average ERPs at each scalp site for each category (smoking, pleasant, neutral) and we will compute the amplitude of the P1 component between 100 and 150 ms over occipital sites [109].

Figure 4. The MDP smartphone task.

The P1 means will be used to estimate AB to smoking vs. neutral and pleasant cues. The steps outlined above for the EEG\ERP data reduction and the statistical analyses will be performed using software (i.e., BESA, MEGIS Software GmbH, Gräfelfing, Germany; Brain Vision Analyzer, Brain Products GmbH, Munich, Germany; SAS 9.2, SAS Institute Inc., Carey, NC) that we have used in previous studies [23,110]. ERP post-processing will be overseen by co-I [name], an expert in EEG and ERP scoring and analysis.

In-Home Smartphone: ABM training and AB assessment. At the end of the Laboratory Session 1, the

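### The dot-probe P1 window is tied to the picture pair and closes before the probe appears, so the smoking-versus-neutral contrast is zero in expectation if trials are labelled by probe position, and otherwise undefined

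*Combined protocol and SAP*

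**What the plan says.** All references are to the combined protocol and SAP.

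- **Laboratory sessions: ERP data collection and reduction.** EEG is "segmented into 700-ms segments starting 100 ms before onset of the picture or word pair". The reference level is likewise tied to the pair: it comes from the 100 ms ahead of it, with no separate rule for the probe. The plan then takes "average ERPs at each scalp site for each category (smoking, pleasant, neutral") and says "we will compute the amplitude of the P1 component between 100 and 150 ms over occipital sites". The resulting means are to estimate bias to smoking against neutral and pleasant cues. Pair onset is the only timing event this section names.
- **Laboratory sessions: AB assessment using the MDP task.** In each trial "two pictures, of smoking and neutral content, will be displayed simultaneously on either side of the fixation cross for 200 ms". The pictures then go off and a probe takes the place of one of them. Probe position is random and balanced over the two picture types, and picture side is random and balanced over left and right. The reaction-time score labels a trial by the picture the probe replaces.
- **Justification & Feasibility (the account of ERP measures of bias).** The lead supporting dot-probe study is described as finding that "probes replacing fearful faces produced significantly larger occipital P1 than probes that replaced neutral faces".
- **Exploratory Aims and Exploratory analyses.** The ERP work, including the P1, is exploratory.

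**The concern.** A P1 contrast between smoking and neutral trials is informative only if the two kinds of trial differ by the time the P1 is measured. Every MDP trial shows one picture of each kind. What separates the trials is where the probe lands, and the P1 window as written closes before that happens.

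The section on Innovation presents the ERP measure as a main strength of the study. Under Potential Problems & Alternative Strategies, a P1 that fails to distinguish bias leads to a search of later components (P2, N2, P3). A P1 contrast that is zero for reasons of timing would trigger that search, and it could be reported as evidence that training has no early attentional effect.

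**Working it through.** **1. The plan's own trial count.** The ERP section gives 320 trials.
- MDP: 16 pairs x 10 repeats = 160 (also 4 blocks x 40).
- Stroop: 80 neutral + 80 smoking = 160.
- Sum: 160 + 160 = 320, which reproduces the figure. The MDP alone supplies 160, or 80 per probe type.

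**2. Timing, with pair onset at 0 ms.**
- Segment: -100 to -100 + 700 = +600 ms.
- Probe onset: 200 ms, assuming it follows picture offset at once. Any delay would widen the gap below.
- P1 window as written: 100-150 ms, ending 200 - 150 = 50 ms before the probe.
- The wider P1 peak range in the rationale, 90-160 ms, ends 200 - 160 = 40 ms before the probe.
- P1 evoked by the probe: 200 + 100 to 200 + 150 = 300-350 ms (290-360 ms for the wider range). Both lie inside the segment.

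**3. Expected contrast when trials are labelled by the picture the probe replaces.** Suppose bias adds an amount d to the P1 at the occipital site contralateral to the smoking picture. At any one site, say on the left:
- Mean over smoking-labelled trials = m + d x P(smoking picture on the right) = m + d/2.
- Mean over neutral-labelled trials = m + d/2, because probe position is random with respect to picture side and not yet visible.
- Difference = (m + d/2) - (m + d/2) = 0 for every d.

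This holds at each site separately, not only after pooling left and right. A group-by-session effect is built from these contrasts, so its expectation is also zero.

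**4. Alternatives from the same recording.**
- Same early window, averaged by picture side: site contralateral to the smoking picture minus site contralateral to the neutral picture = (m + d) - m = d.
- Window timed from the probe, labelled by probe type: the full probe effect.

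**5. Simulation check.** 4,000 sessions of 160 trials were simulated, with picture side and probe type crossed at 40 per cell. The true effect (1 unit) and trial SD (5 units) are assumptions that are not in the documents; the SD affects only precision.

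| Scoring | Mean contrast | Simulation SE |
|---|---|---|
| Early window, labelled by probe type, sites pooled | 0.004 | 0.009 |
| Early window, lateralised by picture side | 1.001 | 0.009 |
| Probe-timed window, labelled by probe type | 1.000 | 0.012 |

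**6. Pleasant category.** The MDP has smoking and neutral pictures, and the Stroop has smoking and neutral words. Pleasant pictures occur only in the passive viewing task (Laboratory sessions: EEG assessment of reward sensitivity), which is run at visit 1 and scored there on the LPP.

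**The case against.** The strongest reply is that the text does not fix the reading that produces the zero. The P1 sentence does not repeat its reference event, and no rule assigns an MDP trial to a category. ERPs are kept at each scalp site and picture side is balanced, so a lateralised contrast from the same early window would recover the signal. A reader might infer that the window alone forces a null whatever the analyst does. The documents do not support that: the zero depends on labelling by probe position. What stands is that this is the only trial label the plan uses for the task, that averaging by category without picture side cancels any lateralised signal at each site, and that no lateralised score is specified.

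Three other strong readings also go too far.
- *All P1 results are uninformative.* The Stroop shows one word per trial and supplies 160 of the 320 ERP trials. Its P1 is not affected.
- *The pleasant contrast can never be computed.* The Study overview lists passive viewing among the baseline tasks, and that task includes pleasant pictures. The contrast is impossible only for the MDP and the Stroop.
- *The trial's main conclusions are at risk.* Aim 1 rests on reaction time, Aim 2 on smoking outcomes, and the Power analysis concerns those aims.

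It is also fair to say that early picture-evoked P1 has support in Preliminary Studies, where it separated cigarette-related from neutral pictures at 136-144 ms. But that result compares picture categories with each other and does not address a display that always holds both. Of the three P1 studies in the rationale, two are described as measured to probes; for the third the text does not name the event.

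**Conclusion.** The point holds as a defect in one exploratory analysis. As most naturally read, the MDP P1 contrast has expectation zero in both arms at all three sessions, for any size of true bias. On any other reading it is undefined, because no labelling or lateralisation rule is given. It also departs from the probe-evoked measure on which the rationale relies.

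The conclusion assumes that 100-150 ms counts from pair onset, that the probe follows picture offset, that probe type is independent of picture side, and that trials are not selected on anything that happens after the probe. The first is inferred from the only event the section names. The second and third follow from the task description. The ERP section states no selection on response accuracy.

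No signal is lost under the planned recording, since the probe P1 falls inside the segment. The change is worth making because a null P1 result from the plan as written would say nothing about training.

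**What to change.** In the ERP data collection and reduction section, give the MDP its own rule:

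- Score the occipital P1 100-150 ms after probe onset (300-350 ms after pair onset), separately for probes replacing smoking and probes replacing neutral pictures.
- Name the baseline. The present pre-pair interval can stay. An interval just before the probe would fall during picture display, but picture-evoked activity balances over randomised probe types under either choice.
- If a picture-locked measure is also wanted, average by picture side and score contralateral minus ipsilateral to the smoking picture.
- Remove the pleasant category from the MDP and Stroop P1 contrasts, or limit it to passive viewing at visit 1.
- State the trial count by task: the MDP P1 rests on 160 trials per session, 80 per probe type, so the signal-to-noise argument based on 320 should be made for each task.

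The cost is a few lines of text and minor extra offline processing. The task, the recording, the visits and the sample size do not change.

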Baseline laboratory session: Final eligibility. Participants will be instructed to smoke ad lib prior to their baseline lab session. At the baseline, which will occur within 30 days of the telephone screen, participants will have their smoking status assessed, as a final determinant of eligibility, using expired CO or the NicAlert strip. To determine eligibility with the Major Depression and suicidality criteria, participants will complete the Patient Health Questionnaire-9 (PHQ-9), a reliable and valid self-administered diagnostic instrument that assesses depression severity and risk for suicide [62,63]. Additionally, the subject will be assessed for interest in providing a genetic sample according to procedures described in our IRB-approved genetic banking protocol (Protocol # Lab 09-0099). Any individual who is deemed ineligible for study participation due to the PHQ-9 will be assessed by a master's level counselor and will be given referral recommendations for local psychiatric resources (see "Project SmartMod Mental Health Procedures" in the Appendix, for details). Urine will be collected and tested to evaluate eligibility on the drug use and pregnancy criteria, and participants will be considered ineligible if they are pregnant or have a positive toxicology screen for any of the following drugs: cocaine, opiates, methadone, benzodiazepines, barbiturates, amphetamines, methamphetamines, PCP, or THC. Final eligibility will be determined by the PI, [name], a licensed and credentialed psychologist, and his designated study staff members.

Laboratory sessions: Smoking behavior assessment. Prior to each of the 3 lab sessions, participants may be sent a link to complete the visit questionnaires via email. At each of the 3 lab sessions, participants will provide an expired CO sample, a urine sample to measure cotinine (a tobacco metabolite that measures nicotine exposure) and anabasine (a tobacco metabolite that will allow us to distinguish NRT use from smoking [64]), and complete TLFB [65] to record CPD for the prior seven days at visit 1 and CPD since last visit for visits 2, 3 and each of the telephone counseling sessions. Next, if not previously completed, participants will complete a computerized battery of questionnaires related to smoking behavior. Nicotine

[figure not shown]

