participants will be trained in the use of the smartphone. They will be told that the in-home smartphone ABM training will help them prepare to quit, and that their quit dates will be scheduled for the day after Laboratory Session 2. The participants will be instructed that they can, but are not required to, reduce or eliminate their smoking before their quit date. During the in-home ABM training sessions, participants will complete daily 30-minute training (ABM or sham) and AB assessment sessions on their provided smartphone for 13 days. The 13-day training period was selected because two weeks of in-home training reduced AB in an anxiety study [48]. Participants will be trained on the ABM tasks at the end of the baseline session. The participants will be instructed to complete the task in a quiet, well-lit location in their homes, free from distraction and interruption, at approximately the same time each day. Compliance and accuracy on the training and assessment tasks will be tracked by the program and rewarded by on-screen tallies of money earned at the end of each ABM block. Participants who fail to complete a training and assessment session, or who do so poorly (25% or more incorrect), will receive a message (SMS text or phone call, depending on participant preference) reminding them to complete the training and/or assessment tasks accurately the next day. If a participant fails to complete the task for 2 or more consecutive days, or has 25% or more errors during a training session, a staff member will call him or her to troubleshoot any impediments and encourage training participation.

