In-Home Smartphone: Assessments of Smoking and Craving. At the start of the ABM training, the smartphone will be used to assess daily cigarette consumption and cigarette craving. Participants will be asked to provide the number of cigarettes smoked so far on the day of the assessment, the time that they smoked their most recent cigarette, and a rating of their current “urge” to smoke on a scale from 0 (no urge) to 9 (maximum urge). This single-item measure of craving has been previously used in ecological momentary assessment studies and has been shown to be both reliable and valid (e.g., predictive of subsequent smoking) [111,112]. Additionally, participants will also be asked to provide the amount of caffeine and alcohol that has been consumed each day. Importantly, this assessment will only take about 1 minute to complete, which will minimize burden and allow the participants to immediately proceed to the ABM training.

In-Home Smartphone: Assessment of Training Environment. We will use the smartphone to assess characteristics of the training environment. This will allow us to explore possible relationships between environmental distractions and performance, and also serve as a measure of compliance regarding the instruction to complete the task in a quiet, well-lit location. Throughout the ABM training and assessment period, the smartphone will sample the ambient lighting, background noise levels in dB (no sounds or video will be recorded), and motion (using an accelerometer reading) every 30 s. If the tri-axial accelerometer detects excessive motion, the task will automatically pause at the end of the next block and a message will be displayed reminding the participant to hold the phone still when completing the task. When the motion subsides, the task will resume and the block during which excessive motion was detected will be repeated.

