Exploratory analyses. We will examine the Aim 1 and 2 models covarying the total number of completed ABM or sham training sessions, the number of in-home training sessions completed, in-home training sessions accuracy rates, baseline FTCD, sex at birth, and CPD at each session. We will conduct the following exploratory analyses using multilevel modeling: (1) We will examine the impact of ABM on AB, CPD, and craving assessments collected by smartphone to determine whether the optimal length of training is less than 13 days; (2) We will examine whether individual differences, measured at baseline, predict response to the ABM training on our measures of AB and smoking behavior. These individual differences will include baseline levels of nicotine dependence (i.e., FTND, mCEQ, CPT, and WSWS), mood (i.e., PANAS), anhedonia (i.e., SLIPS), impulsivity (i.e., DDT, SUPPS-P), tolerance to stressors (i.e., DTS and ASI), reward sensitivity (i.e., Passive Picture Viewing), smoking exposure (i.e., CPD and expired CO), gender, handedness (i.e. Chapman Handedness questionnaire), and AB to smoking cues; (3) We will examine whether participants' contingency awareness of the ABM task influenced ABM's effectiveness, because one ABM study with smokers found that only those participants who were aware of the relationship between the probe and stimulus type were responsive to ABM [7]; (4) We will use data about the training environment collected using the smartphone (e.g., location, dB levels, ambient lighting) to examine whether these environmental characteristics influenced ABM's effectiveness; (5) We will use the EEG data collected using our 129-channel sensor net to perform event-related potential (ERP) analyses (including the P1 component), along with source localization analysis to attempt to identify areas in brain that are responsive to ABM. We will preliminarily target occipital regions that have been found to activate in the presence of motivationally salient visual cues [91,124]. (6) We will examine the effects of AB on eye-tracking metrics (e.g., fixation, gaze duration) and compare the reliability of eye tracking with traditional reaction time metrics of AB.

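### The smartphone smoking item is a part-day count taken before each session, but the exploratory training-length analysis treats it as cigarettes per day

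*Combined protocol and SAP*

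**What the plan says.** Section D, under In-Home Smartphone: Assessments of Smoking and Craving, sets the purpose and timing: "At the start of the ABM training, the smartphone will be used to assess daily cigarette consumption and cigarette craving". The item that follows is narrower than that purpose: "Participants will be asked to provide the number of cigarettes smoked so far on the day of the assessment". The phone also asks for "the time that they smoked their most recent cigarette", the current urge to smoke, and caffeine and alcohol intake. No phone item for the previous day's total, or for cigarettes since the last session, is described.

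Under In-Home Smartphone: ABM training and AB assessment, participants are told to do the task "at approximately the same time each day". No clock time or window is given.

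Exploratory analysis (1), under Statistical Approach & Expected Outcomes, reads: "We will examine the impact of ABM on AB, CPD, and craving assessments collected by smartphone". Its purpose is to find out whether the best training length is under 13 days. It is a multilevel model. Session time is not among the covariates listed for the exploratory work, and no offset is mentioned.

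A separate full-day source exists. Under Laboratory sessions: Smoking behavior assessment, participants "complete TLFB [65] to record CPD for the prior seven days at visit 1 and CPD since last visit for visits 2, 3".

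**The concern.** The plan uses the label CPD for a quantity that is not cigarettes per day. The phone counts smoking from the start of the day to the moment the session opens. Someone who trains in the morning reports a small part of the day, and someone who trains late in the evening reports most of it. Whatever is smoked after the session is not recorded by the phone.

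Two things follow for the training-length analysis. A real fall in smoking is shrunk, because only part of each day is seen. Movement in a participant's session hour also changes the count when smoking has not changed. The analysis reads the day-by-day shape of this series to decide how many sessions are needed, so both affect what it is meant to show.

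**Working it through.** The plan gives no figure that depends on the phone count. Its power analyses cover the continuous measures at the three laboratory sessions and the abstinence comparison. There is nothing to reproduce, so the size is shown by illustration.

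**Inputs from the document**
- Part-day count, asked before training (Assessments of Smoking and Craving).
- Training on days 2 to 14, Visit 1 on day 1, Visit 2 on day 15 (Figure 2).
- Visit 2 may be completed up to seven days after its scheduled date (Study overview).
- Entry minimum of 5 CPD, with little cigars counted (Participants).

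**Assumptions not in the document**
- 16 waking hours and an even smoking rate.
- Sessions at 2, 8 or 14 hours after waking.
- Example rates of 15 and 20 CPD beside the entry minimum of 5.

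**Step 1: recorded count.** For a smoker of C cigarettes a day with a session h hours after waking, recorded count = C × h/16.

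| C | 2 h | 8 h | 14 h | Change for a 2-hour shift (C × 2/16) |
|---|---|---|---|---|
| 5 | 0.6 | 2.5 | 4.4 | 0.6 |
| 15 | 1.9 | 7.5 | 13.1 | 1.9 |
| 20 | 2.5 | 10.0 | 17.5 | 2.5 |

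**Step 2: attenuation.** A true reduction of 2 cigarettes a day shows as 2 × h/16, which is 0.25 at 2 h, 1.0 at 8 h and 1.75 at 14 h.

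**Step 3: drift.** If the mean session hour has moved by D hours by a given day, the recorded mean in that arm moves by about (C/16) × D with no change in smoking. The error in the ABM-versus-sham contrast is about (C/16) × (D in ABM − D in sham). It is zero when both arms drift alike and smoke at similar rates. At 15 CPD, each hour of difference between arms adds 15/16 = 0.94 cigarettes.

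**Step 4: what a previous-day item would cover.** Asked on days 2 to 14, it reports days 1 to 13. Day 14 is not covered, and each missed session loses the day before it. The first report concerns day 1, the day of the baseline laboratory visit.

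**Step 5: TLFB recall.** For day 2, recall at Visit 2 on schedule is 15 − 2 = 13 days. At the end of the window it is 15 + 7 − 2 = 20 days.

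**The case against.** The case for leaving this alone has real force.

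- **Reach.** The phone count enters only one exploratory analysis, beside attentional bias and craving. The Aim 2 CPD outcome is a seven-day mean at the laboratory sessions. This stands.
- **Data.** Full-day smoking over the training period is already collected by TLFB at Visit 2. A reader might infer that the trial has lost its post-session smoking data; it has not. The loss is confined to the phone series, which is the source the analysis names.
- **Between-person differences.** The gap between 1.9 and 13.1 cigarettes for the same smoking rate compares early with late sessions. Each participant is asked to keep a steady hour, and subject effects in a multilevel model can absorb stable differences in level. This stands for levels. It does not restore the size of a reduction in cigarettes, which is still scaled by h/16.
- **Randomisation.** Drift shared by both arms largely cancels in the group contrast. This stands. A reader might infer that drift would create a false ABM effect; that needs drift that differs by arm, and the document gives no reason to expect it. Shared drift still distorts the trajectory within an arm.
- **What is missed.** A reader might infer that the phone misses the effect of training by design. It does not. Cigarettes smoked before the next day's session also follow earlier training, so the effect is partly observed.

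It would also go too far to say that the series reflects session hour as much as smoking. The document gives no data on how much session times vary, and the 2-hour shift is an assumption.

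**Conclusion.** The point holds as a measurement error in one exploratory analysis. The phone variable is a part-day count, the plan analyses it as CPD, and nothing stated in the model accounts for session time. Attenuation in cigarettes follows directly: a 2-cigarette reduction shows as 0.25 to 1.75 over the session hours illustrated. Within-person variation in session hour adds noise of unknown size.

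The figures rest on an even smoking rate over 16 waking hours. The direction does not: any smoking after the session is outside the count. The Aim 2 CPD outcome, the abstinence test and the power calculations do not use this variable and are not in question. The correction is worth making because the protocol presents finding the best number of sessions as one of its innovations, and a suitable full-day source is already being collected.

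**What to change.** 1. In exploratory analysis (1), take the CPD trajectory for days 2 to 14 from the Visit 2 TLFB, with the daily entries kept. This also covers days on which a phone session was missed. Cost: recall of about two weeks, or up to about 20 days when Visit 2 falls at the end of its window.
2. Relabel the phone variable as cigarettes so far today. If it is analysed, include session clock time as a covariate or offset. This needs timestamped sessions, which the document does not state, so confirm that they exist.
3. If the app can still be changed, reword the item to ask for the previous day's full-day total of cigarettes and little cigars. Use TLFB for day 14 and for the day before any missed session. Cost: one reworded question and one-day recall.
4. Do not treat the day 1 count as a typical baseline, because it is the baseline laboratory day. Use the seven-day TLFB from Visit 1.
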